10 SAFETY

Observational study Cat. **A** ClinV (Art. 20)

The test subjects are not given medication or tissue samples are taken. No invasive methods are used.

No further security aspects are expected.

10.1 Drug studies

10.1.1 Definition and assessment of (serious) adverse events and other safety related events
ICH: Procedures for eliciting reports of and for recording ... adverse event and intercurrent illnesses.

10.1.2 Reporting of serious adverse events (SAIE) and other safety related events

(KlinV Art. 37)

ICH: Procedures for ... reporting adverse event and intercurrent illnesses.

10.1.3 Follow up of (Serious) Adverse Events

(ICH/EG 6.8.4; SPIRIT #30)

ICH: The type and duration of the follow-up of subjects after adverse events.

10.2 Medical Device Category C studies

10.2.1 Definition and Assessment of (Serious) Adverse Events and other safety related events
(MD: ISO 14155)

10.2.2 Reporting of (Serious) Adverse Events and other safety related events

10.2.3 Follow up of (Serious) Adverse Events

(SPIRIT #30)

10.3 Medical Device Category A studies

This study is a category A clinical observational study in accordance with the Swiss Ordinance on Clinical Trials in Human Research (ClinO: Art. 20).

It is a study with 20 or fewer subjects in each experimental group. The study also focuses on basic findings. The monitoring for quality assurance is carried out by [name]. [name].

SUPSI

10.3.1 Definition and Assessment of safety related events

If a circulatory problem leads to an injury, this is assessed as a safety-relevant event and must be investigated in more detail before continuing the study.

The following are recorded:

- Date and time of the incident
- Incident Procedure
- Persons involved & witnesses Study
- ID (assigned by the CEC)
- Personal details of the person concerned (if not previously recorded)

10.3.2 Reporting of Safety related events

A safety-related event is logged and immediately reported to the sponsor investigator (head of the research laboratory), study leader and supervisor of the study.

The CEC will be informed as soon as possible and appropriate changes to the protocol of the study will be requested. Further explanations on this can be found in chap. 2.10. Safety and protective measures must be reimbursed to the responsible CEC within 2 days .

The report continues to the public liability insurance of Thim van der Laan University College Physiotherapy in Landquart.

SUPSI

11 STATISTICAL METHODS

11.1 Hypotheses & Factors

Subprojects A and B

Subproject A

Jump height (cm)

HO The jump height is not increased by the post-activity cooling compared to thermoneuapplication during a 72-hour recovery period.

H1 The Jump height becomes through the Post-activity cooling increased opposite thermoneutral application during a 72-hour recovery period.

Subjective muscle soreness (VAS)

HO The subjective muscle soreness information is not reduced by post-activity cooling compared to thermoneutral application for 72 hours.

H1 The subjective muscle soreness information is lower due to post-activity cooling compared to thermoneutral application for 72 hours.

Subjective data on general exhaustion (BORG)

HO The subjective information on general fatigue is not reduced by post-activity cooling compared to thermoneutral application for 72 hours.

H1 The subjective data on general fatigue are lower with post-activity cooling compared to thermoneutral application for 72 hours.

Subproject B

MVIC (mV)

HO MVIC performance is measured by the pre-activity cownot increased compared to thermoneutral application for 72 hours

H1 The MVIC Efficiency is increased by pre-activity cooling compared to thermoneutral application for 72 hours

Subjective muscle soreness (VAS)

HO The subjective muscle soreness data is not reduced by the pre-activity cooling compared to thermoneutral application for 72 hours.

H1 The subjective muscle soreness is lower due to the pre-activity cooling compared to thermoneutral application for 72 hours.

SUPSI

Subjective data on general exhaustion (BORG)

H0 The subjective information on general fatigue is not reduced by pre-activity cooling compared to thermoneutral application for 72 hours.

H1 The subjective information on general fatigue is lower due to pre-activity cooling compared to thermoneutral application for 72 hours.

A 2-factor analysis will be carried out in both projects. Factor 1:

Intervention (cooling vs. Thermoneutral application) Factor 2:

Time (0, 24 hours, 48 hours, 72 hours)

11.2 Sample Size

The planned number of 20 subjects (project A), or 20 subjects (Project B) correspond to the group sizes of the comparable cooling studies (cf. (Ascenso et al. 2011, Bailey et al. 2007, Crystal et al. 2013, Rowsell et al. 2009, De Pauw et al. 2014, Guilhem et al. 2013, Jakeman et al. 2009, Howatson et al. 2009, Montgomery et al. 2008, Rupp et al. 2012, Yanagisawa et al. 2003, e.g.).

11.3 Criteria for the statistical use of data in the case of incomplete data sets

Only data from subjects who have completed the entire protocol will be included in the study. This ensures that all data has been collected under the same conditions and thus remains homogeneous and comparable.

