7.4 Discontinuation of study participation

If a participant withdraws from the study, the lot of the allocation is returned to the pot in a new envelope and a new participant is sought.

The already completed consent form is stored in the locked filing cabinet, data that has already been collected is stored, but is not included in the further data analysis of the study.

The conditions for the termination of the experiment were described in chap. 5.4.

There is no disadvantage for the participants if they discontinue their participation in the study.

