8.5 Follow-up treatment of eliminated participants

(ICH/E6 6.5.3; AGEK 9.2; SPIRIT #18b)

I: b) The type and timing of the data to be collected for withdrawn subjects. d) The follow-up for subjects withdrawn from investigational product treatment/trial treatment.

Data already collected from eliminated participants will be stored, but will not be included in the further data analysis of the study.

There is no disadvantage for the participants if they discontinue their participation in the study and no further interventions are necessary for follow-up treatment.

If study participation was due to an injury occurred during study participation,

SUPSI

is aborted, it will be recorded and reported to the sponsor investigator (head of the research laboratory), study leader and supervisor of the study. Furthermore, the report is sent to the public liability insurance of Thim van der Laan University College Physiotherapy in Landquart.

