11.4 Scheduled analyses

11.4.1 Datasets and Data Populations

Only complete data sets will be included in the study. Data that contains only part of the protocol is not included in the analysis. No new subject is being sought to replace the missing data.

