11.4.2 Primary Analysis

The statistical data analysis is carried out by [name]. [name] after completion of the data collection of the respective sub-protocol.

Repeated measures analysis of variance (MANOVA)

2 factors:

Protocol A

Intervention (cooling vs. Thermoneutral application) Time

(0, 24 hours, 48 hours, 72 hours)

SUPSI

Protocol B

Intervention (cooling vs. Thermoneutral application) Time

(0, 24 hours, 48 hours, 72 hours)

The significance level is set at $P < 0.05$, and the statistical data analysis is carried out with SPSS 22.

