11.5 Drop-outs and missing data

If a test subject does not complete the experiment, any data that has already been collected is retained, but is not further incorporated into the final data analysis.

SUPSI

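### The only planned analysis keeps completers alone, which can bias the comparison if loss is related to outcome and differs by arm; the replacement rules in 7.4 and 11.4.1 must also be reconciled

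*Combined protocol and SAP*

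**What the plan says.** Section 11.3 sets the analysis population: "Only data from subjects who have completed the entire protocol will be included in the study". Its stated reason is that the data then stay homogeneous and comparable. Section 11.4.1 repeats the rule: "Data that contains only part of the protocol is not included in the analysis". Section 7.4 says of a participant who withdraws that "data that has already been collected is stored, but is not included in the further data analysis of the study". Section 8.5 reads "Data already collected from eliminated participants will be stored, but will not be included in the further data analysis of the study", and under 11.5 what a drop-out has contributed "is not further incorporated into the final data analysis".

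The only efficacy analysis is in 11.4.2, given as "Repeated measures analysis of variance (MANOVA") with intervention and time (0, 24, 48, 72 hours) as factors. Section 11.4.3 reports no secondary analysis. No analysis of all randomised participants, imputation or sensitivity analysis is described.

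On replacement, 7.4 says that "the lot of the allocation is returned to the pot in a new envelope and a new participant is sought", while 11.4.1 says "No new subject is being sought to replace the missing data".

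**The concern.** A participant who misses only the 72-hour visit loses the 0, 24 and 48-hour values as well. Whether someone completes is settled after the lot is drawn, so the completers are no longer protected by randomisation. The argument in 11.3 concerns uniform measurement conditions and does not address this selection.

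The protocol describes routes by which loss could depend on outcome, and possibly on arm:

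- Section 5.3 lets a participant who does not feel well stop and withdraw.
- Section 8.1.1 lets anyone who feels unwell stop the cold treatment. It does not say that this counts as withdrawal.
- In subproject B the 60% MVIC load follows the application (3.1 and 9.1), so tolerance of the load could depend on temperature.
- In subproject A the exhausting jumps come before the application (9.1), so stopping during them cannot.

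If those recovering worst are lost from the cooling arm, cooling looks better than it is, toward H1 in 11.1. If they are lost from the thermoneutral arm, cooling looks worse.

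**Working it through.** **Inputs.** The plan gives 20 participants per subproject (11.2), four post-intervention times (11.1) and a significance level of 0.05 (11.4.2). It gives no power, SD, effect size or drop-out rate, so there is no planned figure to reproduce. Assumptions: 10 per arm (an even split of 20; sections 6.1 and 10.3 are ambiguous, so 20 per arm is also shown), SD 1, no true effect, two-sided 5% test.

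**(a) Participants lost entirely from one arm, single time point.** If the k people highest on a loss score are removed, and that score has correlation r with outcome, then

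shift = r × (sum of the k largest expected normal order statistics) / (n − k).

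For n = 10 the two largest are 1.539 and 1.001.

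- One lost: 1.539 / 9 = 0.171 SD at r = 1; × 0.3 = 0.051; × 0.5 = 0.085.
- Two lost: (1.539 + 1.001) / 8 = 0.318 SD at r = 1; × 0.3 = 0.095; × 0.5 = 0.159.
- For n = 20 the two largest are 1.867 and 1.408: 1.867 / 19 = 0.098, and (1.867 + 1.408) / 18 = 0.182.

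Simulation (200,000 trials per case, t test, 10 per arm) agrees and adds the error rate:

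| Lost from one arm | r = 0 | 0.3 | 0.5 | 0.7 | 1 |
|---|---|---|---|---|---|
| One: shift (SD) | 0 | 0.049 | 0.087 | 0.119 | 0.171 |
| One: type I error | 5.1% | 5.1% | 5.6% | 6.1% | 7.5% |
| Two: shift (SD) | 0 | 0.094 | 0.159 | 0.223 | 0.318 |
| Two: type I error | 5.0% | 5.5% | 6.4% | 8.0% | 11.6% |

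The right-hand column needs loss fully determined by outcome. At 20 per arm the upper ends are 0.098 SD (6.9%) and 0.181 SD (10.1%). For scale, the difference detectable with 80% power by a two-sample t test is 1.325 SD at 10+10, 1.366 at 10+9 and 1.416 at 10+8.

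A separate check with logistic drop-out on the first post-intervention value (log odds ratio 1 to 2 per SD, within-person correlation 0.6) gave a shift in the four-visit mean of 0.06 to 0.10 SD for 10% versus 0% loss, and 0.12 to 0.18 SD for 20% versus 0%.

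**(b) Same loss in both arms.** The shift is 0. Type I error is 5.2% to 5.7% at r = 0.3 to 0.5, and at most 7.4% (one each) or 9.3% (two each), because removing extremes understates the spread.

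**(c) Only the 72-hour visit missed, in one arm.** Suppose the 48-hour value fully determines who is lost, with within-person correlation ρ from 0.5 to 0.9. Completers-only then moves the four-time mean by

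shift = (shift from (a) at r = 1) × (1 + 3ρ) / 4.

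- One lost: 0.171 × 0.625 = 0.107, rising to 0.171 × 0.925 = 0.158. Simulated: 0.105 to 0.159, type I error 6.4% to 7.4%.
- Two lost: 0.318 × 0.625 = 0.199, rising to 0.318 × 0.925 = 0.294. Simulated: 0.201 to 0.293, type I error 9.1% to 11.1%.

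These are upper ends. At r = 0.3 to 0.5 the same cases give 0.03 to 0.08 SD (one) and 0.06 to 0.15 SD (two).

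A compound-symmetry mixed model on all available values shifts by at most 0.003 SD (type I error 4.9% to 5.2%). An unstructured model with baseline, as proposed under the fix, was also simulated at 10 per arm: shift under 0.01 SD, type I error 4.5% to 5.2%.

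If the unseen 72-hour value causes the loss, some bias remains in the mixed model: 0.01 to 0.03 SD (one) or 0.01 to 0.05 SD (two) in the four-time mean. At 72 hours it is 0.02 to 0.11 or 0.04 to 0.20 SD, against 0.17 or 0.32 SD for completers-only.

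If visits are missed at random in both arms, neither analysis is biased. The completers-only standard error rises by √(10/9) = 1.05 or √(10/8) = 1.12, against at most about 1% when all values are used.

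**(d) No post-intervention value at all.** With loss fully determined by outcome, adjusting for baseline (correlation 0.5, 0.7, 0.9) cuts 0.17 to 0.13, 0.09 or 0.04 SD, and 0.32 to 0.25, 0.18 or 0.07 SD. It does not reach zero.

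**Replacement.** Section 7.4 concerns a participant who withdraws; 11.4.1 concerns missing data. Both can hold if 11.4.1 means only missed visits, but the text does not say so, and a withdrawn participant also leaves incomplete data. Under 7.4 alone the arm counts follow the lots; they are unclear only because 11.4.1 differs.

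**The case against.** The strongest reply is that little may be lost. Follow-up lasts 72 hours and payment comes after the last measurement (9.3.2). Only the right thigh is treated (8.2.1, 8.2.2), fear of cooling and Raynaud's syndrome are exclusions (7.1), and blinding is planned (6.2.2). Nothing in the documents shows that loss will differ by arm. At middle assumptions one loss means 0.05 to 0.09 SD, small beside a detectable 1.32 SD. All of this stands and limits the weight of the point. It does not justify the rule, since each loss is a tenth of an arm of 10 and the discarded data are already stored.

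Replacement under 7.4 would largely remove the loss of precision. It would not remove the selection: the upper ends fall only from 0.17 to 0.16 SD and from 0.32 to 0.27 SD.

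The zero shift in (b) assumes no true effect. With a true effect of 0.8 SD and one outcome-dependent loss rule for both arms, the estimate falls to 0.73 or 0.65 SD. In that example loss is 20% in one arm and 8% to 11% in the other, so it is itself a case of differential loss.

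An unstructured covariance has ten parameters per outcome, which is demanding for about 20 people, and imputation with shifts is more work than a trial of this size might choose. That is why the proposal includes a fallback covariance and leaves the shift settings to the sponsor.

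**Conclusion.** The concern holds and should be fixed. That the plan analyses completers only is certain from the text; the amount of bias is not, because no drop-out rate is given. Under the stated assumptions the bias runs from nothing, through a modest 0.05 to 0.16 SD for one or two losses from one arm at a loss-outcome correlation of 0.3 to 0.5, to 0.32 SD in the extreme case. Keeping all available values nearly removes it when loss follows from observed values, and reduces it otherwise. The replacement wording is a separate, smaller point: the two sections need reconciling, whichever rule is kept.

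**What to change.** Replace the exclusion wording in 7.4, 8.5, 11.3, 11.4.1 and 11.5 with:

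> The primary analysis includes all randomised participants in the arm drawn, using every available post-intervention measurement (0, 24, 48, 72 hours) as far as the consent allows. Each outcome is analysed by a linear mixed model for repeated measures (SPSS MIXED, REML) with intervention, time, intervention × time and baseline; unstructured covariance, or compound symmetry if that does not converge; and a small-sample degrees-of-freedom method if available. Participants with no post-intervention value are reported by arm with reasons. In a sensitivity analysis their values are multiply imputed by regression on baseline and arm, then shifted toward worse in one arm at a time, in steps of 0.25 SD, until the conclusion changes or 2 SD (VAS, BORG: the 0-10 limit) is reached. Completers-only is a sensitivity analysis.

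Merge 7.4 and 11.4.1 into one replacement rule, and say how it fits the limit of 40 participants in the synopsis. Whichever rule is chosen, keep a replaced participant's available data in the allocated arm as far as the consent allows. The protocol should also state whether and how participants who stop the application are followed; no such rule is proposed here.

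**Cost.** This needs protocol wording reviewed by the ethics committee under 2.10, and perhaps matching participant information (2.7). Use of data after withdrawal depends on consent text that was not available for this review. No visits or measurements are added, the data are already stored, and SPSS is already named. The main result would then rely on missing at random, with the residual shifts shown in (c). The arms may be slightly unequal, and people with no post-intervention value are covered only by the sensitivity analysis. The 0.25 and 2 SD settings are assumptions for the sponsor to confirm.

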11.4 Scheduled analyses

11.4.1 Datasets and Data Populations

Only complete data sets will be included in the study. Data that contains only part of the protocol is not included in the analysis. No new subject is being sought to replace the missing data.

11.4.2 Primary Analysis

The statistical data analysis is carried out by [name]. [name] after completion of the data collection of the respective sub-protocol.

Repeated measures analysis of variance (MANOVA)

2 factors:

Protocol A

Intervention (cooling vs. Thermoneutral application) Time

(0, 24 hours, 48 hours, 72 hours)

SUPSI

Protocol B

Intervention (cooling vs. Thermoneutral application) Time

(0, 24 hours, 48 hours, 72 hours)

The significance level is set at $P < 0.05$, and the statistical data analysis is carried out with SPSS 22.

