Statistical Considerations:	
The effectiveness of cooling on recovery and performance are tested on:
 
Repeated measures analysis of variance (MANOVA) factors:
 
Protocol A
 
- Task (Cooling vs. Thermoneutral application)- Time (These factors are measured immediately after cooling and 24 hours, 48 hours and 72 hours after the interventions) 
Protocol B
 
Task (cooling vs. thermoneutral application)
 
Time (These factors are measured immediately after cooling and 24 hours, 48 hours and 72 hours after the interventions)
 
The significance level is $P < 0.05$, the statistical data analysis is carried out with SPSS 22.

GCP Statement:	This study will be conducted in compliance with the protocol presented here, the current version of the Declaration of Helsinki, the ICH-GCP, ISO EN 14155 (as far as authoritative), and the Swiss Human Research Ordinance HFV.

SUPSI

Overview of the study

Cold therapy, such as cold water immersions and ice packs, has long been known as post-activity recovery strategies. Sports with different levels of intensity lead to different levels of exhaustion of the body's musculoskeletal, neuronal and metabolic systems. Exercise can also lead to microscopic injuries in muscle tissue, colloquially known as muscle soreness. In sports physiotherapy and rehabilitation, cold therapy has long been used as a post-activity intervention to alleviate these subjective symptoms. This is also confirmed by the current scientific knowledge base (Ascenso et al. 2011, Banfi et al. 2010, Crystal et al. 2013, Delextrat et al. 2013, u.a.). Cold therapy is usually referred to as a procedure which aims to alleviate pain symptoms and inflammatory processes.

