Post-activity cooling (subproject A) - In this subproject, the influence of post-activity cooling compared to thermoneutral application on recovery is determined. It is investigated whether the maximum jump height changes between these interventions after maximum performance in the form of vertical jumps (1 min) and 20 min of sustained cooling or thermoneutral application (direct, 24 hours, 48 hours, 72 hours after the interventions). To investigate this, the test subjects are tested before the maximum performance (1 min vertical jumps) and again directly, 24 hours, 48 hours and 72 hours after cooling/thermoneutral application. In order to be able to determine the baseline and measure the effect of cooling compared to the thermoneutral application, the test subjects must each perform 3 vertical, maximum jumps. The maximum vertical jump height is used as an objective recovery factor in this subproject. Weilert, this subproject investigates the extent to which the subjective muscle soreness and general exhaustion data of the test subjects differ within the cooling group and thermoneutral group. To this end, before and inach the maximum performance (1 min vertical jumps) measured the subjective information of the test subjects (direct, 24 hours, 48 hours, 72 hours after cooling/thermoneutral application). A 0 - 10 VAS and 0 - 10 BORG scale is used. The VAS and BORG data are used as a subjective recovery factor in this subproject.

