Preactivity cooling (subproject B) - In this subproject, the influence of preactivity cooling compared to thermoneutral application on performance is determined. It is investigated whether the MVIC of the ventral thigh muscle changes between these interventions after submaximal performance in the form of 60% MVIC (1 min) of the ventral thigh muscle and preceding 20 min of cooling or thermoneutral application. In order to determine the baseline and to investigate the effect of cooling on the MVIC, MVIC is determined via an EMG measurement and on the Cor 1 before loading. Following the MVIC determination, 60% of the MVIC is determined. Afterwards, the subjects will perform a submaximal isometric contraction (60% MVIC) for 1 min. Before this submaximal load, the test subjects receive cooling or a thermoneutral application. Following the submaximal load and 24 hours, 48 hours and 72 hours after the load, MVIC is tested again. MVIC will be subproject as objective performance factors. Furthermore, this study examines the subjective Muscle soreness as well as the general state of exhaustion before and after cooling (directly, 24 hours, 48 hours, 72 hours after the interventions). This is done with a 0-10 VAS and a 0-10 BORG scale. The VAS and BORG data are used as subjective performance factors in this subproject .

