6.1 Study design and justification

Randomized, controlled, double-blind study

It is an observational study of Cat. A (ClinO, Art. 20), whereby a tested medical device is tested on young, healthy volunteers during the intervention.

The group size of the participants is 40 people each (sub-protocols A & B) and 20 respectively people (subproject A) and 20 people (subproject B).

The group classification of the test setup to be tested (cooling vs. thermoneutral application) will be randomized.

Blinding of the participants is ensured by the use of a thermoneutral application. The examiners are blinded by the addition of another examiner who operates the apparatus. The responsible statistician is blinded and has no access to the personal data of the test persons and is not present when the data is collected.

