9.1 Schedules of the various protocols

1. *Subject Information & Informed Consent*

10 Min

2. *Preparation of the subject*

15 min

3. *Running the Test Log (Sublogs)*

Partial Protocol A: first measurement + intervention - approx. 60 min	
Cooling vs. Thermoneutral application on recovery	
Cooling panel	Thermoneutral Application Group
1. 3 x Vertical Leaps VAS & BARROW (max 5 min)	1. 3 x Vertical Jumps, VAS & BARROW (max 5 min)
Max 1 min break	Max 1 min break
2. 1 minute max vertical Leaps, VAS & BARROW (1 min)	2. 1 minute max vertical jumps, VAS & BARROW (1 min)
Max 5 min break	Max 5 min break
3. Cooling (20 min)	3. Thermoneutral application (20 min)
Max 1 min break	Max 1 min break
4. 3 x Vertical Leaps, VAS & BARROW (max 5 min)	4. 3 x Vertical Jumps VAS & BARROW (max 5 min)
Directly after the Intervention	immediately after the intervention
5. 3 x Vertical Leaps, VAS & BARROW (max 5 min)	5. 3 x Vertical Jumps, VAS & BARROW (max 5 min)
24 hours after the intervention	24 hours after the intervention
6. 3 x Vertical Jumps, VAS & BARROW (max 5 min)	6. 3 x Vertical Jumps, VAS & BARROW (max 5 min)
48 hours after the intervention	48 hours after the intervention
7. 3 x Vertical Leaps, VAS & BARROW (max 5 min)	7. 3 x Vertical jumps, VAS & BARROW (max 5 min)
72 hours after the intervention	72 hours after the intervention

SUPSI

Partial Protocol B: first measurement + intervention - approx. 60 min	
Cooling vs. Thermoneutral application on performance	
Cooling panel	Thermoneutral Application Group
1. 1 x MVIC, VAS & BORG (max 3 min) Max 1 min break	1. 1 x MVIC, VAS & BORG (max 3 min) Max 1 min break
2. Cooling (20 min) Max 1 min break	2. Thermoneutral application (20 min) Max 1 min break
3. 60 % MVIC for 1 min (2 min) Max 5 min break	3. 60 % MVIC for 1 min (2 min) Max 5 min break
4. 1 x MVIC, VAS & BORG (max 5 min) immediately after the intervention	4. 1 x MVIC, VAS & BORG (max 5 min) immediately after the intervention
5. 1 x MVIC, VAS & BORG (max 5 min) 24 hours after the intervention	5. 1 x MVIC, VAS & BORG (max 5 min) 24 hours after the intervention
6. 1 x MVIC, VAS & BORG (max 5 min) 48 hours after the intervention	6. 1 x MVIC, VAS & BORG (max 5 min) 48 hours after the intervention
7. 1 x MVIC, VAS & BORG (max 5 min) 72 hours after the intervention	7. 1 x MVIC, VAS & BORG (max 5 min) 72 hours after the intervention

Sub-protocol	Total time commitment	Visits
A	Approx. 80 min	Once 60 min and 3 times for max 5 min

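### Baseline is measured in order to judge the effect of cooling but never enters the primary analysis, which costs precision in arms of about 10

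*Combined protocol and SAP*

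**What the plan says.** Section 9.1 has the outcomes measured at step 1, before load and application: three jumps with VAS and BORG in subproject A, and "1 x MVIC, VAS & BORG (max 3 min") in subproject B. They are repeated directly after (step 4) and at 24, 48 and 72 hours (steps 5 to 7). That makes five occasions.

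Section 3.1 gives the purpose of the first one. For A, the three jumps are done "In order to be able to determine the baseline and measure the effect of cooling compared to the thermoneutral application". For B: "In order to determine the baseline and to investigate the effect of cooling on the MVIC, MVIC is determined via an EMG measurement".

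The analysis has four time levels, not five. Section 11.1 gives "Time (0, 24 hours, 48 hours, 72 hours") and section 11.4.2 repeats "0, 24 hours, 48 hours, 72 hours", each with Intervention as the only other factor. The synopsis fixes the meaning of the first level: "Time (These factors are measured immediately after cooling and 24 hours, 48 hours and 72 hours after the interventions"). No covariate, change score or baseline time level is named, and section 11.4.3 has no secondary analysis.

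**The concern.** The baseline has a stated role in measuring the effect and no role in the analysis. In a two-factor model without it, stable differences between people (some jump higher, some contract harder) stay in the error term of the group comparison.

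This matters because the trial is small and cannot easily grow. The synopsis caps the total at 40 for financial reasons, and section 11.2 justifies the number only by comparison with other studies, without effect size, SD or power. Keeping only completers (sections 11.3 and 11.5) may shrink the arms further. The baseline is already being collected, so leaving it out may give up precision that costs nothing to obtain. If it is not pre-specified, adding it later becomes a choice made with the data in view.

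**Working it through.** **Which occasion is omitted.** Read alone, the 0 in sections 11.1 and 11.4.2 could mean baseline. The synopsis says it is the measurement directly after the application, and sections 3.1, 4.1 and 5.1 list the same four moments. The omitted occasion is therefore step 1.

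**No plan figure to reproduce.** The documents give no power calculation, SD or correlation.

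**Inputs.** From the documents: 20 participants per subproject (section 11.2), significance level 0.05, four post times. Assumed: 1:1 allocation, so 10 per arm and N = 20; a two-sided test; an Intervention effect averaged over the four times; SD of a single measurement = 1; and, at first, one correlation r among baseline and post values.

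**Formulas.**
- Variance of a person's mean of four post values: V = (1 + 3r)/4.
- With baseline as covariate, including the cost of estimating its slope: (V − r²) × (1 + 1/(N − 4)) = (V − r²) × 1.0625.
- SE of the group difference: √(2 × variance/10). Power and detectable difference use the noncentral t, with 18 df unadjusted and 17 adjusted.

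**Example, r = 0.7.** V = 3.1/4 = 0.775. Adjusted: (0.775 − 0.49) × 1.0625 = 0.303. The variance ratio is 0.303/0.775 = 0.39, so the SE ratio is 0.63 and the gain is worth 1/0.39 ≈ 2.6 times the sample. At r = 0.5: V = 0.625, adjusted 0.398, ratio 0.64, worth about 1.6 times the sample.

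| r | Variance ratio | SE ratio | Detectable difference at 80% power (SD), planned → adjusted | Power for 0.8 SD, planned → adjusted |
|---|---|---|---|---|
| 0 | 1.06 | 1.03 | 0.66 → 0.69 | 92% → 90% |
| 0.3 | 0.86 | 0.93 | 0.91 → 0.85 | 69% → 75% |
| 0.5 | 0.64 | 0.80 | 1.05 → 0.84 | 57% → 76% |
| 0.7 | 0.39 | 0.63 | 1.17 → 0.73 | 49% → 86% |
| 0.8 | 0.26 | 0.51 | 1.22 → 0.63 | 45% → 95% |

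**Baseline predicting less well than the post values predict each other.** Baseline is rested and the 0 h value follows a hard load, so this is plausible. Keep the post-post correlation at 0.7 (V = 0.775) and let the baseline-post correlation b vary, with b² in place of r²:

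| b | Variance ratio | Detectable difference (SD) | Power for 0.8 SD |
|---|---|---|---|
| 0.5 | 0.72 | 1.17 → 0.99 | 49% → 62% |
| 0.4 | 0.84 | 1.17 → 1.07 | 49% → 55% |
| 0.3 | 0.94 | 1.17 → 1.13 | 49% → 51% |
| 0.2 | 1.01 | 1.17 → 1.17 | 49% → 48% |
| 0 | 1.06 | 1.17 → 1.21 | 49% → 46% |

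Break-even is where (V − b²) × 17/16 = V, that is b = √(V/17) = √(0.775/17) = 0.21.

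**Arm size.** Section 6.1 also says "The group size of the participants is 40 people each (sub-protocols A & B"), which conflicts with 20 per subproject and must be reconciled. With 20 per arm (penalty 1 + 1/36; 38 and 37 df) the detectable difference goes from 0.72 to 0.56 SD at r = 0.5 and from 0.80 to 0.49 SD at r = 0.7. The conclusion is the same.

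**Validity.** In simulations under no effect (20,000 trials per setting), the rejection rate was 4.7% to 5.0% without baseline and 4.6% to 5.2% with it. The unadjusted estimate matched the true difference to within 0.005 SD.

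**Covariate or change score.** A change score has variance V + 1 − 2r. At r = 0.3 that is 0.475 + 1 − 0.6 = 0.875, which is 0.875/0.475 = 1.84 times the unadjusted variance. The covariate is the safer choice.

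**The case against.** The plan contains no error in this respect. H1 in section 11.1 compares the groups over 72 hours, not change from baseline, and a comparison of randomised groups answers it. Section 3.1 says why baseline is measured but does not promise adjustment, and in B the baseline MVIC also sets the 60% load. All of that stands, and it is why the point concerns precision only.

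The gain also needs the Intervention main effect to be the test of H1, which the documents do not say. If the Intervention × Time interaction were the test, stable differences between people would already cancel and baseline would add little. This stands too. But the interaction cannot show an effect that is constant across the four times, and the wording of H1 fits the main effect better.

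The equal-correlation table is the favourable case. The second table shows smaller gains, still positive down to b of about 0.21.

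Coverage is uneven: four of the six hypotheses concern VAS or BORG, where rested ratings in healthy volunteers may sit near 0. MVIC appears in mV, mVs and Nm in different sections and rests on a single baseline trial, so its correlation is harder to guess than that of jump height. These points reduce the expected gain without removing the case for the change.

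**Conclusion.** The concern holds, as an improvement the sponsor should make and not as a flaw that invalidates the test. The documents collect baseline for a stated purpose that the analysis does not serve.

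The size depends on correlations the documents do not give. Over the range shown, the SE falls by 37% at a common r of 0.7 (SE ratio 0.63), by 20% at 0.5 (0.80) and by 7% at 0.3 (0.93). It rises by 3% if baseline is uninformative. The gain is likeliest to be substantial for jump height, and for MVIC if its baseline predicts well.

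The finding that the planned test is unbiased is limited to the omission of baseline. Analysing completers only (sections 11.3 and 11.5) and returning a withdrawn participant's lot to the pot (section 7.4) are separate matters that it does not cover.

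**What to change.** In sections 11.1 and 11.4.2, before any data are seen:

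1. Define 0 h as the measurement directly after (section 9.1, step 4).
2. Add the participant's own step 1 value as a covariate to a model with Intervention, Time and Intervention × Time over the four post times. For jump height, use the best of the three baseline jumps.
3. Name the baseline-adjusted Intervention effect as the test of each H1.
4. For VAS and BORG in A, use the rating listed with the load and before the application: "1 minute max vertical jumps, VAS & BARROW (1 min") at step 2. It precedes the application and may vary more between people than a rested rating. In B the application comes before the load, so only the rested rating exists and little gain should be expected.
5. State which MVIC variable is analysed, so that its baseline is defined on the same scale.

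The cost is a few lines of text and one degree of freedom per model. No measurement is added. The worst case is about 6% more variance if baseline predicts nothing.
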